3.1. Study Objectives

3.1.1. Primary Efficacy Objective

To estimate the treatment effect of pirfenidone 2403 mg/d on lung function.

3.1.2. Secondary Efficacy Objective

To estimate the effectiveness of pirfenidone on IPF patients’ functional capability and quality of life.

3.1.3. Exploratory Efficacy Objective

To estimate the effectiveness of pirfenidone on the frequency and number of acute exacerbations of IPF and on features of HRCT.

3.1.4. Safety Objective

To evaluate the safety of pirfenidone.

3.2. Endpoints

3.2.1. Primary Efficacy Endpoint

- Change from Baseline to Week 26 in absolute mL forced vital capacity (FVC) and % FVC

3.2.2. Secondary Efficacy Endpoints

- Change from baseline to Week 26 in 6-minute walk test (6MWT) distance
- Change from baseline to Week 26 in patients’ quality of life as measured with European Quality of Life 5-Dimension Questionnaire (EQ-5D)

3.2.3. Exploratory Efficacy Endpoints

- Frequency and number of IPF exacerbations

**ML39355_STATISTICAL ANALYSIS PLAN_Final 2.0_17 June 2020**

- CT scan evaluation (semiquantitative assessment "HRCT fibrosis score". The high-resolution computed tomography (HRCT) findings will be evaluated using HRCT scoring system. Interstitial lung disease (ILD) radiologist will make assessment of 4 main findings in three zones of each lung. The six zone scores will be averaged to determine the total score for each patient at baseline and at Weeks 26 and 52)

3.2.4. Safety Endpoints

- Treatment-emergent adverse events (AEs)
- Treatment-emergent serious adverse events (SAEs)
- Change from baseline in clinical laboratory parameters and electrocardiogram (ECG) parameters

4. Study Design**4.1. General Study Design and Plan¹**

This is a local, multicenter, interventional, non-randomized, non-controlled, non-comparative, open-label study to assess the effectiveness of pirfenidone in patients with IPF in Russian clinical practice. Approximately 60 patients diagnosed IPF will be enrolled to receive pirfenidone 2403 mg/d for 26 weeks. No comparator group is implied in the study.

For enrolment into the study, the diagnosis of IPF must be confirmed by central review of HRCT scans and of the surgical lung biopsy (SLB) samples, if available (if performed prior enrolment in routine clinical practice). The HRCT scans will be reviewed by one or two central readers who are radiologists with expertise in IPF. If the first expert (central reader-1) agrees with the local opinion, the second expert (central reader-2) will not review scans. If the first expert disagrees with the local opinion, the second expert should review scans. Histopathological (SLB) samples will be reviewed by the one central reader who is a pathologist with expertise in IPF. All other diagnostic procedures will be performed and assessed at a local level.

Eligible patients aged 40–80 years must have a confident clinical and radiographic/ or histological diagnosis of IPF according to 2011 IPF guidelines (ATS 2011). Patients with possible UIP on high-resolution computed tomography and without SLB in case of “working diagnose” of IPF during multidisciplinary team (MDT) discussion, are also eligible for the trial (see Table 2).

Patients will be required to have a relative %FVC ≥ 40 %, percent predicted carbon monoxide diffusing capacity (%DLCO) ≥ 30 %, and able to walk ≥ 100 meters during the 6-minute walk test at the Screening.

All assessments in the study will be initiated only after signed Informed Consent is obtained from the patient. For this purpose, an additional visit may be performed prior to the start of the Screening procedures and an appropriate review of the patient’s clinical data relevant to the IPF diagnosis is done.

Any patient identified for the study must discontinue all prohibited therapies including therapy targeted to treat IPF for at least 28 days before the start of the treatment period. Other than

¹ This section is based on the sections 3.1 “Description of the study”, 3.2 “End of study and length of study” of the clinical study Protocol.

**ML39355_STATISTICAL ANALYSIS PLAN_Final 2.0_17 June 2020**

permanent use of corticosteroids (prednisolone at a maximum daily dose of 15 mg or equivalents) and brief periods of corticosteroid use for acute IPF exacerbation, patients will not receive any other therapy for the treatment of IPF. After central review of HRCT and SLB, patients will enter the Screening period, which may last up to 28 days (4 weeks).

After the Screening, eligible patients will enter the Treatment period lasting 26 (\pm 1) weeks. All patients will receive pirfenidone 2403 mg/d administered orally in divided doses three times per day (TID) with food. Dose of the study treatment will be titrated over 14 days to the full dose of 9 capsules per day (three 267 mg capsules taken orally TID with food). Patients will remain on a stable maintenance dose for the duration of the treatment period unless the dose is reduced to manage adverse events or titrated again when restarting study treatment after an appropriate interruption in treatment.

The primary efficacy endpoint in the study is the change from baseline to Week 26 in absolute (mL) FVC and relative (%) FVC as measured by spirometry procedure. Spirometry will be performed at the Screening, on Day 1 of treatment, at Week 12, Week 26 and in the extended Follow-up period (Weeks 39 and 52), if applicable. At screening, spirometry measurements will be performed before and after administration of albuterol (or salbutamol) from a metered dose inhaler. During further visits, bronchodilator test is not necessary to perform. Spirometry data collected throughout the study will be evaluated by local readers.

Patients will have a telephone assessment at Week 1, when safety-related information and adherence to treatment is collected. Subsequently patients will have in-clinic visits at Weeks 2, 4, 8, 12, 16, 20 and 26. Patients should complete an adverse event and dosing compliance diary between all visits. Additionally, telephone calls to patients will be scheduled at Weeks 3, 5, 7, 13 and 24 as a part of IPF care program. A total of 5-7 calls are scheduled in the study, including extra-calls at Weeks 8 and 10 as needed.

Treatment with pirfenidone will continue until Week 26 (\pm 1). Patients will be followed through the Follow-up visit scheduled 2-4 weeks after treatment completion or until entry into the long-term follow-up (rollover study), whichever occurs earlier. Patients who undergo lung transplantation or who chose to withdraw from study procedures early will be followed for vital status until Week 26. If patients discontinue study treatment early for any reason, they should continue with all scheduled study procedures through Week 26.

Patients who complete participation in the study prematurely due to any reasons (drop-outs) will not be replaced.

Patients who proceed until Week 26 in the study and are compliant with the study treatment, may continue treatment with commercially available pirfenidone after study completion in real clinical practice (long-term follow-up or rollover study). In this case, patients will have two follow-up assessments of FVC and 6MWT at Weeks 39 and 52 and CT scans evaluation at Week 52. Information on AEs occurrence will also be collected during the rollover part of the study.

If a patient cannot participate in the rollover part of the study for any reason, a follow-up visit will be performed 14-28 days after the last dose of pirfenidone is taken.

A schedule of activities is provided in Table 1.

An Independent Data Monitoring Committee (IDMC) will be implemented in the study. The

ML39355_STATISTICAL ANALYSIS PLAN_Final 2.0_17 June 2020

IDMC will conduct regular review of the trial safety data, with the focus on death cases, serious adverse events, unexpected adverse events, adverse events leading to treatment or study discontinuation, liver enzyme increases, reported as adverse events, and other AEs immediately reported to the Sponsor.

Duration of participation in the study for an individual patient is between 31 and 35 weeks (excluding long-term follow-up). For patients continuing in the rollover study the duration of participation in the study extends up to maximum 58 weeks.

ML39355_STATISTICAL ANALYSIS PLAN_Final 2.0_17 June 2020

Study period	IC Visit	Screening (Washout, if applicable)	Treatment period									Follow-Up	Long-Term Follow-Up ¹⁶		
			Day 1	W1 (± 1 d)	W2 (± 2 d)	W4 (± 2 d)	W8 (± 2 d)	W12 (± 1 w)	W16 (± 1 w)	W20 (± 1 w)	W26 (± 1 w)		14–28 days after last dose	W39 (± 2 w)	W52 (± 2 w)
Week (Window)		-4 to -1													
Borg scale ¹³		x	x					x			x	x		x	x
EQ-5D questionnaire ¹³		x	x					x				x			x
Patient diary (review, dispense) ¹⁴			x	x	X	x	x	x	x	x		x			
Telephone calls (IPF Care program) ¹⁵															

¹ Written informed consent must be obtained prior to any study-associated procedure, including discontinuing any prohibited medications.

² Safety-related information (AEs) and adherence to treatment is collected.

³ Complete medical history is collected at an IC visit, washout and screening only. Thereafter, directed history (including review of AEs/SAEs, concomitant medications, oxygen use, hospitalizations, dosing, and diary) is only collected.

⁴ Complete physical examination is performed at the Screening only (head, eyes, ears, nose, and throat, and the cardiovascular, dermatological, musculoskeletal, respiratory, gastrointestinal, genitourinary, and neurological systems). At subsequent visits (or as clinically indicated), only limited, symptom-directed physical examinations should be performed.

⁵ Height is assessed at the Screening only.

⁶ ECG should be performed after patient's resting in a supine position for at least 10 min, prior to other procedures scheduled at that same time (e.g., vital sign measurements, blood draws), bronchodilator administration and within 3 hours after any meal)

⁷ To confirm IPF will be applicable to use previously performed HRCT, if it is performed not earlier than 24 months before the Screening. Review of the SLB samples obtained within 4 years before the Screening should be performed centrally for eligibility confirmation. Histopathological evaluation, if not available, is not repeated at the Screening.

⁸ Transbronchial biopsy or BAL are not mandatory and will only be reviewed at the Screening, if available, to exclude other causes of PF.

⁹ HRCT should be performed at the Screening only for patients having no validated procedure within 2 months prior initiation of treatment.

¹⁰ At screening, spirometry measurements of FVC should be performed before and after administration of albuterol (or salbutamol) from a metered dose inhaler (4 separate doses of 100 mg). Tests should be repeated after a 15-min delay. During further visits, bronchodilator test is not necessary to perform. Collection and recording of the retrospective FVC values obtained in clinical practice over the last year will be performed only at the screening visit.

¹¹ Blood samples must be drawn in fasted state. Serologic tests: rheumatoid factor, anticyclic citrullinated peptide and antinuclear antibody titer.

¹² Pregnancy test must be performed before first dosing on Day 1 and must be negative. If the urine test is positive, serum pregnancy test must be performed.

¹³ Questionnaires should be self-administered before the patient or clinician receives any information on disease status, prior to the performance of non-PRO assessments, and prior to the administration of study treatment, with the exception for Borg scale administered in conjunction with the 6MWT.

¹⁴ Patient diary should be filled out on daily basis by the patient and reviewed by the investigator at in-clinic visits. Patient diary captures information on compliance and AEs occurrence and is dispensed as needed.

¹⁵ Schedule of calls in IPF Care Program you can see in Appendix 7

¹⁶ Only in patients continuing treatment with pirfenidone in real clinical practice.

4.2. Randomization and Blinding²

Randomization is not planned in the study.

Blinding is not applicable in this open-label study.

5. Sample Size³

Taking into account study design (single group prospective study), sample size was estimated based on feasibility of patient enrollment with precision-based approach. In the ASCEND study primary efficacy endpoint (Percent Predicted FVC) in pirfenidone group changed from 67.8 (11.24) (denoted as mean (SD)) at baseline to 65.3 (14.52) at week 26, with stable disease (decline in FVC < 10 % to 0 %) in 60.1 % of study patients.

The required sample size for two-sided 95% confidence level can be calculated using the following formula:

$$n = \hat{p}\hat{q} \left(\frac{Z_{\alpha/2}}{E} \right)^2 ;$$
$$n = 0.601 \times 0.399 \left(\frac{1.96}{0.125} \right)^2 \approx 58.96.$$

Assuming previous calculations, 60 patients included in the study will be sufficient for study parameters estimation. Taking into account study goals and the notion that the study drug is a product for the treatment of an orphan drug, margin of error of 0.125 is considered sufficient for parameter estimation. For precision-based sample size justification, with a sample size of 60 patients, an expected mean value of 2.5% and standard deviation of 20, distance from the mean to limit of the two-sided 95% confidence interval for the mean Change from Baseline to Week 26 (Percent Predicted FVC) will extend about 5 (margin of error). The SD for change from baseline at week 26 is conservatively estimated based on the results of the ASCEND study as standard deviation for Percent Predicted FVC in pirfenidone group at week 26 (14.52) multiplied by $\sqrt{2}$ (Machin et al., 1997). This is also in line with the results of CAPACITY programme (Noble et al. 2011) in which the SD of changes from baseline was 17 - 20 at week 72.

Taking into account an expected rate of screening failures about 45%, up to 109 patients will be screened for eligibility.

6. General Considerations

6.1. Timing of Analyses

No interim analysis is planned in this study.

² This section is based on the section 4.2 “Method of treatment assignment and blinding” of clinical study Protocol.

³ This section is based on the section 6.1 “Determination of sample size” of clinical study Protocol.

ML39355_STATISTICAL ANALYSIS PLAN_Final 2.0_17 June 2020

6.2. Analysis Populations

The main patient samples of interest are defined as follows.

The ‘All enrolled patients’ set will consist of all patients who:

Gave their Informed Consent.

The ‘Allocated to treatment’ set will consist of all patients who:

Gave their Informed Consent and

Had successfully completed Screening procedures.

The ‘Treated set’ (TS) will consist of all patients who:

Were in the ‘Allocated to treatment’ set and

Received any dose of the study treatment.

The ‘Full analysis’ set (FAS) will consist of all patients who:

- Were included in the ‘Treated’ set and
- Had data for at least one post-baseline assessment of any efficacy measurement.

The ‘Complete case set’ (CCS) will include FAS patients who

- Provided FVC data at 26-week assessment.

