4.5.13.5 Weeks 2, 4, and 8 (\pm 2 Days)

The following procedures will be performed at Weeks 2, 4, and 8:

- Directed history (including review of AEs/SAEs, concomitant medications, oxygen use, hospitalizations, dosing)
- *ECG (at Weeks 4 and 8 only)/ All ECGs are to be obtained prior to other procedures scheduled at that same time (e.g., vital sign measurements, blood draws) and should not be obtained within 3 hours after any meal.*
- Physical examination, vital signs, and weight
- Clinical laboratory assessments, including hematology, serum chemistries, and pregnancy test for women of childbearing capacity (pregnancy test at Weeks 4 and 8 only)
- Review patient's diary

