4.5.13.6 Weeks 12 (\pm 2 Days)

The following procedures will be performed at Week 12:

- Directed history (including review of AEs/SAEs, concomitant medications, oxygen use, hospitalizations, dosing)
- EQ5D questionnaire (should be performed before any other non-PRO assessments)

Pirfenidone—F. Hoffmann-La Roche Ltd

- Physical examination, vital signs, and weight
- Clinical laboratory assessments, including hematology, serum chemistries, and pregnancy test for women of childbearing capacity
- Spirometry (FVC)
- 6MWT and Borg Scale
- Review patient's diary

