6.3. Missing Data⁴

For missing FVC data imputation, patients will be classified into different patterns depending on the availability of data:

Patients with a 26 week FVC value:

1. those who received study drug until 26 weeks (completed the treatment period);
2. those who prematurely discontinued study drug, but who were followed up until Week 26.

Patients without a 26 Week FVC value:

3. those who were alive at 26 weeks;
4. those who died before 26 weeks.

Missing data at other visits before Week 26 (primary outcome variable) will not be imputed.

The following imputation methods including sensitivity analyses will be applied for patients with pattern 3 - 4:

Assuming that deaths of the patients (pattern 4) is likely to be related to worsening of IPF, these unobserved FVC values should be lower than those in patients who did not die prior to Week 26.

Methods for handling missing data due to death will include the following:

- Replacement with the worst possible value (FVC= 0 mL or 0%) (Primary analysis).
- Replacement with worst observed averaged FVC value at week 26 (Sensitivity analysis).

⁴ This section is based on the section 6.2 “Summaries of conduct of study” of clinical study Protocol.

ML39355_STATISTICAL ANALYSIS PLAN_Final 2.0_17 June 2020

- Replacement with an intermediate value (FVC =1500 mL or 50%) (Sensitivity analysis).

Missing data due to reasons other than death (e.g., missing visits, early withdrawal from the study, including missing values due to lung transplantations) (pattern 3) will be replaced with imputed values based on the average measurements for “similar” patients at that time point. Similar patients are those without missing data before that time point and whose data have the smallest sum of squared deviations (SSD) from that patient for all visits prior to the one with the missing data. Missing data due to lung transplant will be imputed using the SSD method even if the patient dies after lung transplant.

The procedure referred to as the sum of squared deviations (SSD) is outlined as follows:

Step 1: For post-Baseline missing value to be imputed at a visit (Visit week 26) for a particular patient (Patient A), a set of all patients without any missing values for visits from Baseline up to Visit week 26 as Patient A will be selected.

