7.5. Prior and Concurrent Medications⁹

eCRF form: “PRIOR/ CONCOMITANT MEDICATIONS”.

⁸ This section is based on the section 4.5.2 “Medical History and Demographic Data”, 6.3 “Summaries of Demographic and Baseline characteristics” of clinical study Protocol.

⁹ This section is based on the section 6.2 “Summaries of conduct of study” of clinical study Protocol.

ML39355_STATISTICAL ANALYSIS PLAN_Final 2.0_17 June 2020

1. Prior and concomitant medications will be analyzed based on the information from the Concomitant/Prior Medications (CM) domain.

2. All prior and concomitant medications will be coded using the World Health Organization Drug Dictionary (WHODD) version B2 March 2018 (or further updating) according to Data MATRIX SOP [4].

Classification of treatment as either Prior or Concomitant will be based on stop date of medication in “PRIOR/CONCOMITANT” eCRF form. The number (%) of patients reporting the use of any medications, and the number of reported medications will be presented in separate tables by pharmacological subgroup (3rd level) and chemical substance (5th level).

Medications that stop prior to the date of first dose of study therapy will be classified as Prior medications. If a medication stops on or after the date of first dose of study therapy (or “ONGOING”) then the medication will be classified as Concomitant. For patients who take part in the rollover study, medications started on or after the date of the first dose of the study drug during the rollover study will be summarized separately.

3. If the information about stop date of medication is missing or incomplete, the rules from section 6.3 will be applied for classification. Medications will be assumed to be concomitant, unless there is clear evidence (through comparison of partial dates) to suggest that the medication stopped prior to the first dose of study therapy. If there is clear evidence to suggest that the medication stopped prior to the first dose of study therapy, the medication will be assumed to be Prior.

By-patient listings will be provided.

8. Efficacy Analyses¹⁰

eCRF form: “SPIROMETRY”.

Descriptive statistics for all efficacy variables will be presented by visit. For the descriptive statistics, the rules presented in section 7 will be applied.

The FAS and Complete case set will be used for the efficacy analysis. Analysis on Complete case set will be one of the sensitivity analyses to be performed.

All efficacy data will be listed.

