**ML39355_STATISTICAL ANALYSIS PLAN_Final 2.0_17 June 2020**

two separate days at Week 26, if either is missing, the non-missing value will be used. If both values are missing, the data will be imputed as specified in Section 6.3.

Data will be analyzed using standard descriptive statistics for continuous variables and 95% CI for the means and mean changes.

The data imputation methods for primary endpoint are described in Section 6.3.

For the primary analysis, missing data due to death will be replaced with the worst possible value (FVC= 0 mL or 0%). Missing data due to reasons other than death (pattern 3) will be replaced with imputed values based on the average measurements for “similar” patients at that time point (SSD, Primary analysis).

As sensitivity analyses, the following imputation methods will be used:

1. Missing data due to death will be replaced with the worst observed FVC value at week 26. Missing data due to reasons other than death (pattern 3) will be replaced with imputed values based on the average measurements for “similar” patients at that time point (SSD).

2. Missing data due to death will be replaced with an intermediate value (FVC =1500 mL or 50%). Missing data due to reasons other than death (pattern 3) will be replaced with imputed values based on the average measurements for “similar” patients at that time point (SSD).

3. Missing data due to death will be replaced with the worst possible value (FVC= 0 mL or 0%). Missing data due to reasons other than death (pattern 3) will be replaced with LOCF.

4. Missing data due to death will be replaced with the worst observed FVC value at week 26. Missing data due to reasons other than death (pattern 3) will be replaced with LOCF.

5. Missing data due to death will be replaced with an intermediate value (FVC =1500 mL or 50%). Missing data due to reasons other than death (pattern 3) will be replaced with LOCF.

6. Missing data due to death and due to reasons other than death (pattern 3) will be replaced with LOCF.

Analysis of the primary efficacy endpoint will be also repeated on the Complete case set (CCS) without missing data imputation as the sensitivity analysis. Complete case set will include patients related to pattern 1 and 2 (section 6.3), results will be reported for pattern 1 and 2 separately and overall.

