Path to the program code, date and time of output

Data extracted: DD.MM.YYYY

ML39355_STATISTICAL ANALYSIS PLAN_Final 2.0_17 June 2020

 F. Hoffmann-La Roche Ltd
 ML39355

Table 1.3 Analysis populations

 Allocated to treatment set
 Page X of X

	Total (N = XX) n (%)
Allocated to treatment	XX (100%)
Treated set (TS)	XX (XX.X)
Full analysis set (FAS)	XX (XX.X)
Completed case set (CCS)	XX (XX.X)

N: the number of patients in the Allocated to treatment set.

n: the number of patients within a specific category. Percentages are calculated as $(100 \times n/N)$.

Treated set: patients from 'Allocated to treatment' set, who received any dose of the study treatment.

Full analysis set: patients from 'Treated' set, who had data for at least one post-baseline assessment of any efficacy measurement.

Completed case set: patients from 'Full analysis' set, who provided FVC data at 26-week assessment.

Path to the program code, date and time of output

Data extracted: DD.MM.YYYY

ML39355_STATISTICAL ANALYSIS PLAN_Final 2.0_17 June 2020

 F. Hoffmann-La Roche Ltd
 ML39355

Table 1.4 Study visits
 Allocated to treatment set
 Page X of X

	Total (N = XX) n (%)	Within visit window n (%)
Treatment period		
Start of Treatment (Day 1)	XX (XX.X)	N/A
Week 1 Telephone Assessment (+/- 1 day)	XX (XX.X)	XX (XX.X)
Week 2 (+/- 2 days)	XX (XX.X)	XX (XX.X)
Week 4 (+/- 2 days)	XX (XX.X)	XX (XX.X)
Week 8 (+/- 2 days)	XX (XX.X)	XX (XX.X)
Week 12 (+/- 2 days)	XX (XX.X)	XX (XX.X)
Week 16 (+/- 1 week)	XX (XX.X)	XX (XX.X)
Week 20 (+/- 1 week)	XX (XX.X)	XX (XX.X)
1st day at Week 26 (+/- 1 week)	XX (XX.X)	XX (XX.X)
2nd day at Week 26 (+/- 1 week)	XX (XX.X)	XX (XX.X)
Follow-up Visit (14-28 days after last dosing)	XX (XX.X)	XX (XX.X)
Long Term Follow-Up/Rollover Study		
Week 39 (+/- 2 weeks)	XX (XX.X)	XX (XX.X)
Week 52 (+/- 2 weeks)	XX (XX.X)	XX (XX.X)

N: the number of patients in the Allocated to treatment set.

n: the number of patients within a specific category. Percentages are calculated as (100 x n/N).

Path to the program code, date and time of output

Data extracted: DD.MM.YYYY

ML39355_STATISTICAL ANALYSIS PLAN_Final 2.0_17 June 2020
Protocol Deviations

 F. Hoffmann-La Roche Ltd
 ML39355

Table 1.5 Protocol deviations / violations

Allocated to treatment set

Page X of X

	Total (N = XX)
	n (%)
Patients with at least one protocol deviation	XX (XX.X)

N: the number of patients in the Allocated to treatment set.

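### The FAS drops treated patients who die before the first efficacy visit at Week 12, so the primary death rule (FVC = 0) never reaches them

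*SAP*

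**What the plan says.** **Who is analysed.** SAP 6.2 and Protocol Section 6 admit to the FAS those in the Treated set who also "Had data for at least one post-baseline assessment of any efficacy measurement". The footnote to SAP Table 1.3 repeats the condition ("who had data for at least one post-baseline assessment of any efficacy measurement"). Neither document makes an exception for death. SAP Section 8 states: "The FAS and Complete case set will be used for the efficacy analysis". The complete case set is a subset of the FAS.

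**When efficacy is measured.** Protocol 4.5.13.5 ("The following procedures will be performed at Weeks 2, 4, and 8") lists history, ECG, examination, laboratory tests and diary, but no FVC, 6MWT, Borg scale, EQ-5D or HRCT. Protocol 4.5.13.6 ("The following procedures will be performed at Week 12") is the first post-baseline visit with spirometry, 6MWT, Borg and EQ-5D. HRCT returns at Week 26. The Appendix 1 schedule agrees.

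**How deaths are handled.** Pattern 4 in SAP 6.3 is death before 26 weeks with no Week 26 FVC value, and no minimum follow-up is required. The stated reasoning is that "these unobserved FVC values should be lower than those in patients who did not die prior to Week 26". The primary analysis (SAP 8.1) therefore sets FVC to 0 mL or 0%. One exception is written: "Missing data due to lung transplant will be imputed using the SSD method even if the patient dies after lung transplant". Tables 2.3 and 2.6 each have a row that counts death before Week 26, and both are FAS tables.

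**The concern.** The death rule covers deaths before Week 26, but the entry condition to the analysis set removes the earliest ones first. A patient who dies in Week 11 adds nothing to the primary mean. A patient who dies in Week 13, after a Week 12 assessment, adds minus the whole baseline value. Neither document gives a reason for this cut-off.

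Under the primary 0% rule the omission can only favour the drug. It also lowers the death rows of Tables 2.3 and 2.6. Table 2.17 counts exacerbations only if fatal (SAP 8.3) but is run in the FAS, so a fatal exacerbation with death before Week 12 would normally be missing there too.

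The six imputation sensitivity analyses and the visit-window and complete-case analyses all sit inside the FAS, so none recovers these patients. Those who merely stop the drug are not affected, because Protocol 3.1 asks them to keep attending scheduled procedures to Week 26.

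**Working it through.** **Plan's own figures (SAP Section 5).** n = 0.601 × 0.399 × (1.96/0.125)² = 58.96, planned as 60. Half-width for the mean change = 1.96 × 20/√60 = 5.06, stated as about 5. Both reproduce.

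**Inputs.** 60 treated; mean change in the others -2.5 points (the planned 2.5, taken as a decline); SD 20; planning baseline 67.8% and Week 26 mean 65.3% (SD 14.52), all from SAP Section 5. The 40% entry floor is from Protocol 4.1.1. One-year mortality of 5.6% (GAP stage I) and 16.2% (stage II) is from Protocol Appendix 6.

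**Shift in the mean per omitted death, 0% rule.** A death at baseline b contributes -b:

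-2.5 - [59 × (-2.5) - b]/60 = (b - 2.5)/60

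| Baseline b | Shift per omitted death |
|---|---|
| 40% | 0.63 |
| 50% | 0.79 |
| 67.8% | 1.09 |
| 80% | 1.29 |

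Two deaths at 67.8%: 2 × 65.3/60 = 2.18. The shift is positive for every eligible baseline. In mL the documents give no planning values. Assuming a mean baseline of 2000 to 3000 mL and a 100 mL decline in the others, one omitted death is worth (2000 - 100)/60 = 32 to (3000 - 100)/60 = 48 mL.

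**Confidence interval, one death at 67.8%.**
- Omitted: n = 59, mean -2.5, SD 20, half-width 5.21, interval -7.7 to 2.7.
- Included: mean (59 × (-2.5) - 67.8)/60 = -3.59; SD 21.55; half-width 5.57; interval -9.2 to 2.0.

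**Other death rules, one omitted death.**

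| Rule | b = 67.8% | b = 40% |
|---|---|---|
| Worst observed value | 0.56 | 0.10 |
| 50% | 0.26 | -0.21 |
| LOCF | -0.04 | -0.04 |

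The worst-observed row assumes normal Week 26 values: expected minimum of 59 draws = 65.3 - 2.313 × 14.52 = 31.7%. The 50% rule reverses sign at b = 40% because 50% is above that baseline.

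**Row for decline of at least 10% or death.** With k other patients in the row, the loss per omitted death is (k + 1)/60 - k/59: 1.67 percentage points at k = 0 and 1.38 at k = 10.

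**How likely is an early death?** The documents give no count, so this is an assumption. At constant hazard, risk over 12 of 52 weeks = 1 - (1 - m)^(12/52).

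| Assumed hazard | Risk per patient | Expected of 60 | P(at least one) |
|---|---|---|---|
| Quarter of stage I | 0.33% | 0.20 | 18% |
| Half of stage I | 0.66% | 0.40 | 33% |
| Stage I | 1.32% | 0.79 | 55% |
| Stage II | 4.0% | 2.4 | 91% |

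The reduced hazards allow for the exclusions in Protocol 4.1.2, such as life expectancy under 12 months.

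**The case against.** **The two rules do not contradict each other.** One defines the set and the other fills gaps within it, and moving efficacy from the Treated set to the FAS was an explicit amendment decision. That is so. The criticism is that, run together, they limit the death rule to patients who lived long enough to be measured.

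**A fatal exacerbation might itself count as an efficacy measurement.** It is an exploratory efficacy endpoint, and a CT taken to diagnose it could also qualify the patient. An unscheduled assessment would indeed admit a patient. Treating an adverse-event record as an efficacy assessment is strained, and would still leave out other early deaths.

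**The Listing 1 shell proves little.** It has a row with Treated yes, FAS no and reason Death, but it is a mock row without a death date. It is consistent with this reading and is not needed for it.

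**The effect is conditional and modest.** It is zero without early deaths, the two intervals above largely overlap, and the primary analysis is descriptive with no comparator or threshold. The 91% figure takes all 60 patients as stage II at full hazard. These points stand and limit the severity.

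**The exclusions are already visible.** Table 1.3, Listing 1 and Tables 3.10.1 and 3.14 would show them. They do not correct the primary mean or the death rows.

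**Admitting only deaths makes entry depend on outcome.** Unmeasured living withdrawals stay out. With six of them, one death moves the mean by 65.3/54 = 1.21 rather than 1.09. The asymmetry is real, but it is far smaller than the error of omitting the death. Death is an observed outcome with a value fixed by the plan; a living withdrawal's FVC is unknown.

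**Conclusion.** The concern holds and should be fixed. As written, a treated patient who dies before Week 12 with no unscheduled efficacy measurement escapes the primary death rule and every planned efficacy sensitivity analysis. At the planning baseline each such death flatters the primary mean by 1.09 points, which is 1.09/2.5 = 44% of the expected change and about a fifth of the planned half-width.

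This size rests on 60 treated patients, a mean change of -2.5 in the others and the 0% rule. Under the alternative death rules the shift is smaller and can reverse slightly. Whether any early death occurs is unknown from the documents. Cases missing because of lung transplant are outside the point, since the plan sends them to SSD.

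**What to change.** Add *or died before Week 26* to the second FAS condition in SAP 6.2 and Protocol Section 6. Equivalently, include all treated patients who died before Week 26 in Tables 2.2, 2.3 and 2.17 and in the death row of Table 2.6. Then:

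- Apply the existing death rules, with transplant cases left under SSD.
- For sensitivity analysis 6 (LOCF for deaths), report how many deaths have only a baseline value, because LOCF gives them zero change.
- Report treated patients outside the FAS by reason.
- Keep the current FAS as a sensitivity analysis.

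Tables 2.18 and 2.19 need no change, since they cover rollover patients only. Imputing living patients who have only a baseline value is not required.

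**Cost.** A protocol amendment (Protocol 9.6) and an SAP revision, which SAP Section 2 allows before database soft lock. No visits or data are added: deaths are already recorded (Protocol 5.3.5.7), and vital status to Week 26 is followed for patients who withdraw from procedures (Protocol 3.1). A death after consent is withdrawn may stay unknown (Protocol 4.6.1), and that patient remains outside the FAS. The estimate may be less favourable and slightly less precise: with one early death at baseline 67.8% the half-width goes from 5.2 to 5.6.
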